Failure to adapt intervention for delivery in UK setting	Evaluation and implementation teams have clear plans for the adaptation of the intervention involving those who have developed and modified the original MDFT for delivery in different settings, intervention who have previously adapted the intervention for delivery in settings outside the US, key stakeholders including those with experience of delivering substance use interventions in the UK and those in receipt of substance use interventions, either directly (young people) or indirectly (parents/ carers). We are confident an appropriately, culturally sensitive adapted version will be available.

Failure to create an intervention that is culturally sensitive to the community	In adapting the intervention, a key objective will be to ensure MDFT considers cultural sensitivity. The adaption group involves young people, carers and stakeholders that represent the community within the sites. Barnardo's has a clear commitment to EDI and ensuring intervention delivery takes account of the diversity of potential participants, they have a great deal of experiencing in producing culturally sensitive interventions.
Failure to engage stakeholders in project set-up and delivery	Evaluation and implementation stakeholders have positive, constructive relationships and communication is ongoing. As the project progresses the evaluation team will make site visits to discuss processes with the intervention team.
Families in the control group might receive a range of interventions from different providers. This may overlap with interventions delivered as part of MDFT	Data will be collected to monitor what interventions are being delivered and by whom in the BAU group as part of the pilot study. Data from the sites to date suggests that while several providers deliver substance misuse services, both NHS and non-statutory, this tends to be based on 1:1 and group approaches involving motivational interventions and psychoeducation. The use of intensive, family-based interventions is rare in young people's substance use services in the UK. We do not anticipate any contamination within the study.
Trial does not recruit to target	The process of recruitment is an outcome of interest in a pilot study rather than a threat to validity. We will monitor key recruitment criteria and explore, through qualitative interviews key barriers and facilitators associated with recruitment, ensuring that lessons learnt are incorporated within the efficacy study. The evaluation team have extensive experience of recruiting participants in RCT's involving substance using adolescents and have consistently achieved recruitment targets.

Not recruiting sufficient therapists to deliver MDFT may impact on recruitment in the trial.	We have allowed for a three-month lead in to recruit therapists for the trial. Barnardo's has demonstrated experience in recruiting specialist staff to deliver specialist interventions in the target sites and have key contacts with organisations within the community to identify staff.
Trial does not retain sufficient participants at the final end point	We estimate 90% of eligible and consenting participants will be available at the 6-month endpoint, a figure to be reviewed at the end of the pilot study. Evaluation staff have multiple strategies for retaining young people in research studies including payments for outcome completion, collection of multiple contact methods and the use of co-locators. In other studies, involving similar populations the target retention rate has been achieved and, in some cases, exceeded.
Therapists not retained.	Therapist retention will be monitored in the MDFT group at both sites. Barnardo's have specific strategies to retain staff and as MDFT is not delivered currently within the UK opportunities for staff to move to new services are limited.
The random nature of selecting young people could be seen by some as unethical.	we are in a state of equipoise regarding the effects of the intervention. Control group participants will receive established BAU that is current practice in accordance with the Declaration of Helsinki. No participant will be disadvantaged by being allocated to BAU.
Young people may not want to consent to being part of study resulting in lack of numbers for the evaluation	Young people will have access to a clear information sheet highlighting the need to evaluate a new service. Information will be reviewed by a young person's advisory group who will provide input on how best to engage young people in the research. Our experience of other studies with similar populations is that many young people are motivated by altruism, the opportunity to contribute to services that will help others in a similar position in the future.

The potential that young people, therapists and researchers experience negative impacts of participating in the study.	All staff and researchers have access to supervision to raise issues relating to the trial. We will implement a reporting system to allow all staff, young people and their carers and researchers to highlight any potential adverse events and, if needed, seek support. We will implement an independent DMEC to review adverse and iatrogenic effects as they arise and if they believe these are directly attributable to the trial and severe in nature, they will raise the potential of stopping the trial with the research team and funder.
Families may be resistant to participating in the trial.	We have extensive experience of including marginalised populations in evaluations. The pilot study will explore qualitatively barriers to participation. All information about the trial will be available in advance of consent and potential participants provided an opportunity to discuss participation. Consent will be based on the consent of the young person rather than the family and early work in delivering MDFT identifies the most appropriate family members to be involved in the delivery of MDFT.
Young people may exhibit demoralisation if randomised to BAU rather than the MDFT intervention.	Clear information to participants that the study involves a state of equipoise, that at this stage we have no evidence that MDFT is better than BAU and this is what is being tested. Disengagement and 'faking bad' are key signs of resentful demoralisation and both concepts will be explored qualitatively with young people.
Sites may drop out of the study due to changes locally related to financial issues or leadership.	All sites have a track record of commitment to the delivery of services and an understanding of research. Senior sign off has been secured at all sites and commitment made to deliver the research as planned.
Imposition of COVID, or similar, restrictions	Both the delivery team and research team have contingency plans for remote working.
Poor quality delivery of MDFT	Fidelity and quality assurance are monitored throughout the study through the MDFT portal. Therapists are supervised both on-site and by staff from MDFT international. Regular

	reports relating to fidelity on the part of the therapist, adherence on the part of participants and quality assurance are made available and reviewed. Issues can be identified quickly and remedial action taken.
Participants do not complete questionnaires because they are too long	The outcome battery has been used in similar populations and takes on average 15 minutes to complete at baseline and 25 minutes at follow up. Response from other studies suggest burden will not be an issue.

Timeline

05/25 - 09/25: Adapt MDFT for delivery in UK, trial set-up, ethics, registration, recruitment of supervisors and therapists.

09/25 – 12/25: Conduct internal pilot with 60 participants recruited.

06/26: Evaluate transition criteria and submit transition report form.

07/26 - 05/27: Recruit 340 to efficacy study.

01/27 – 11/27: Conduct efficacy 6-month follow-up.

07/27 – 05/28: Conduct efficacy 12-month follow-up.

06/28: Analyse results.

09/28: Submit final report

Bibliography

- BALDWIN, S. A., CHRISTIAN, S., BERKELJON, A. & SHADISH, W. R. 2012. The effects of family therapies for adolescent delinquency and substance abuse: a meta-analysis. *J Marital Fam Ther*, 38, 281-304.
- BLACK, C. 2020. review of Drugs evidence relating to drug use, supply and effects, including current trends and future risks. London: HMSO.

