While the prevalence of drug use is similar across ethnicity, except for Asian populations who have a lower prevalence (OR 0.39; 95% CI 0.19 to 0.81), the proportion of those receiving treatment is far lower, 5% of ethnic minorities versus 89% White British. Reasons for this disparity include lack of awareness of available services, lack of culturally sensitive services and a lack of trust stemming from previous negative experiences with services (Pinto et al., 2024). Furthermore, the complexities of intersectionality's of marginalised communities also play a role in an individual's openness to engage, and experience of, a range of support and statutory services from healthcare to the justice system (Healy and Colliver, 2022).

Multidimensional family therapy (MDFT) is widely delivered across the United States, Netherlands, Belgium, Sweden, Finland, Lithuania and Aruba, although there is no current MDFT provision in the UK. MDFT is an integrative, family-based, multiple systems-oriented intervention specifically designed to address adolescent problems including substance use, mental health, aggressive and violent behaviour and delinquency (Liddle, 1991, Liddle et al., 2005). MDFT's aim is to reduce substance use, improve mental health and enhance developmental functioning across several behavioural domains:

- 1. the adolescent domain helps adolescents to engage in treatment, regulate their emotions, communicate with, and relate effectively to, their parents and other adults, and to develop social competence and alternative behaviours to drug use.
- 2. the parent domain engages parents in therapy, increases their behavioural and emotional involvement with their children and improves parental practices.
- 3. the family interactional domain focuses on reducing conflict and improving emotional attachments and patterns of communication and problem-solving using multi-participant family sessions.
- 4. the extrafamilial domain fosters family competency within all social systems in which the adolescent participates.

The intervention is manualised and delivered by trained therapists through individual and family sessions.

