The proposed research aims to address key questions about the efficacy of MDFT, adapted for use within the UK using a mixed method, two-arm, prospective, individually randomised controlled trial comparing MDFT versus business as usual (BAU). The trial will have an embedded internal pilot to address key questions regarding the parameters for a definitive efficacy study and a concurrent implementation and process evaluation addressing important questions regarding the MDFT intervention in detail.

Intervention

Delivery of MDFT will occur between July 2025 and July 2027. MDFT aims to reduce substance use, improve behavioural issues and reduce young people's involvement in the criminal justice system through multidimensional family therapy. Greater detail on the theoretical framework is available here https://www.mdft.org and a theory of change diagram and narrative provided in figure 2 and appendix I. It is delivered by a qualified MDFT therapist, and it intervenes in four connected areas: (i) the young person, (ii) the parents, (iii) the family, and (iv) the community. The main activities that drive behavioural change are (i) individual therapy sessions between the therapist and young person (typically 8-20 individual sessions), (ii) parent sessions between the therapist and parents (typically 4-10 sessions), (iii) family sessions where the therapist facilitates meaningful conversations among the family members who attend (typically 4-10 sessions), and (iv) sessions between the family and social systems in their community (typically 4-10 community sessions/meetings). Additional activities outside of the session promote individual change, and phone calls to the young person and parents support the development of problem-solving skills for when difficulties in relationships arise.

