As part of the recruitment process Barnardo's will work with a variety of referral agencies to ensure equity of opportunity to engage in the research. Referral and recruitment data will be carefully monitored in terms of ethnicity, sex and disability status, including an assessment of those eligible but refusing consent, this will provide an early indication of any issues that may arise due to the recruitment practices.

Table 1: Trial design

Trial design, i	ncluding number of arms	Multidimensional Family Therapy to reduce alcohol and drug use in adolescents, an individually, two-arm randomised controlled trial with embedded internal pilot.		
Unit of r	andomisation	Individual young person		
Stratification variables (if applicable)		Geographic area (Bristol, Newport) Severity of substance use (Low/ medium risk, high risk) assessed using the GAIN-SS		
Duimour	variable	Percent days abstinent from alcohol and drugs		
Primary outcome	measure (instrument, scale, source)	Time line follow-back in the 28 days prior to the 6 month follow up.		
Secondary outcome(s)	variable(s)	Percent days abstinent from alcohol and drugs in the 28-days prior to the 12-month follow up Self-reported volume of violent offending behaviour at months 6 & 12. Behaviour: internalising behaviour (emotional regulation plus peer relationships subscales), externalising behaviour (hyperactivity plus conduct problems subscales) at months 6 & 12. Mental health and wellbeing at months 6 & 12. Alcohol and substance use problems at months 6 & 12.		

		Self-report Client Service Receipt Inventory (CSRI) to assess police involvement at months 6 & 12 (arrests, cautions, charges, court attendance), educational outcomes (suspensions, exclusions, managed moves) and employment status.		
	measure(s) (instrument, scale, source)	Offending: Self-report delinquency scale covering the previous 6-month (SRDS), violent offences are classed as carrying a weapon, robbery, assault, racial assault and fire setting. Behaviour: Strengths and difficulties questionnaire (SDQ), externalising behaviour and internalising behaviour. Mental health and wellbeing, Warwick-Edinburgh Wellbeing Scale-short form (WEMWBS-SF). Alcohol and substance use problems, European School Project on Alcohol and Drugs Problem Scale (ESPAD-PS). Self-report Client Service Receipt Inventory (CSRI).		
Baseline for	variable	Percent days abstinent from alcohol and drugs.		

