primary outcome	measure (instrument, scale, source)	Single substance use question assessing the 28 days prior to baseline.		
Baseline for secondary outcome	variable	Volume of self-reported offending in the 6 months prior to baseline. Behaviour: internalising behavior and externalising behaviour at baseline. Mental health and wellbeing at baseline. Family cohesion and conflict at baseline. Alcohol and substance use problems at baseline. Self-report Client Service Receipt Inventory (CSRI) in the 6 months prior to baseline to assess police involvement (arrests, cautions, charges, court attendance), educational outcomes (suspensions, exclusions, managed moves) and employment status.		
	measure (instrument, scale, source)	Offending: Self-report delinquency questionnaire covering the previous 6-month (SRDS).		

Behaviour: Strengths and difficulties questionnaire (SDQ). internalising behaviour and externalising behaviour.

Mental health and wellbeing, Warwick-Edinburgh Wellbeing Scale-short form (WEMWBS-SF).

Family: Brief Family Relationship Scale (BFRS).

Alcohol and substance use problems, European School Project on Alcohol and Drugs Problem Scale (ESPAD-PS).

Self-report Client Service Receipt Inventory (CSRI).

Randomisation

The randomisation of young people to MDFT or BAU will be conducted by research staff after informed consent has been taken and the baseline assessment completed, by intake staff at Barnardo's. The allocation will involve an equal probability of receiving one of the two trial arms, MDFT or BAU, and will employ random permuted blocks of variable size (2, 4 or 6) with a random block seeded throughout. Randomisation will be conducted using a secure, independent randomisation service, Sealed Envelope Ltd. Randomisation will be stratified by geographical site (Bristol, Newport) and severity of substance use (low/ medium, high) ascertained using the GAIN-SS assessed at baseline. A full quality assurance AUDIT trail will be kept of all allocations and research staff will not be able to see future allocations. The allocated group will be relayed back to staff in the sites.

It is not possible, or appropriate, to blind young people or staff to their allocated group although follow-up at months 6 will be conducted by researcher's blind to participant allocation.

Participants

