Consent and baseline assessment will be conducted by staff employed by Barnardo's they will be conducted in a safe, therapeutic and convenient location for the young person, this will include facilities managed by Barnardo's, community facilities accessed as part of community partnerships, children's services, school and the young person's home. Data will be collected on-line, and randomisation will be conducted independent of Barnardo's by research staff after baseline data collection has been conducted.

Inclusion criteria

- 1. Young people aged 13-17 years inclusive who are resident in the Bristol or Newport LA.
- 2. Currently involved with the police or youth justice service or at risk of offending.

At risk of offending defined as having at least one of the following risk factors, assessed on referral.

- Previously being in the secure estate.
- Currently, or previously, persistently absent from school (defined by DfE as 10% or more).
- Have been the victim of violence.
- Currently, or have attended alternative education provision.
- Received multiple suspensions from school or has been permanently excluded.
- Have a sibling or parent who has been involved in serious violence or identified as facing exploitation harm.
- Currently, or have been, in the care system.
- Have been identified as being at risk of criminal exploitation.
- Currently or have had a social worker.
- Have previously been in contact with youth justice services.
- Have been arrested, admitted an offence and released by the police with no further action.
- 3. Evidence of alcohol or substance use on at least 4 occasions in the past 28 days, assessed using a single substance use frequency question on referral to Barnardo's.
- 4. Willing and able to provide informed consent or willing to provide assent with a parent/ carer willing to provide consent.

Exclusion criteria:

- 1. Alcohol or substance severity that requires inpatient residential treatment or immediate detoxification.
- 2. Severe mental health condition requiring immediate psychiatric assessment.

Figure 3: Flow chart of recruitment processes.

Referral partners identify young people who would be suitable for MDFT

Referral partners share information with Barnardo's through secure referral form.

Barnardo's contacts young person to assess frequency of substance use, check eligibility, and gauge interest, share information sheet and privacy notice

If willing to take part young person attends for baseline assessment

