On completion of assessment battery research staff receive automated message of a referral, randomisation conduct, allocation relayed back to Barnardo's staff who either initiate MDFT or make referral to BAU.

Randomised to BAU (200) Randomised to MDFT (200)

YP referred to alternative service YP allocated MDFT therapist

Outcome assessment at month 6 Outcome assessment at month 6 (n=182) (n=182)

Outcome assessment at month 12 Outcome assessment at month 12 (n=160) (n=160)

Data is collected at 6- and 12-months using bespoke, secure, on-line data collection system and transferred to secure servers managed by the University of Kent. Six- and 12-month data collection is completed by research staff blind to participant allocation and participants receive a payment of £25 for completing assessments at baseline 6- & 12 months.

Sample size calculations

Sample size estimation was conducted in STATA18. A clinically important effect size for substance use frequency in adolescents is estimated as 0.27, similar to the lower bound

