estimates found in systematic reviews of MDFT (Filges T. et al., 2018, van der Pol et al., 2017b). This equates to a number needed to treat of 6, where at least one in six participants receiving MDFT would show clinically important benefits, and a difference in the frequency of substance use of at least 13% in the MDFT group. Detecting an effect size smaller than this provides no additional benefit, the commissioning of services in England and Wales requires the service to achieve a clinically important difference for the target population. To detect this difference, with power at 80% and alpha of 0.05 and a two-tailed test, requires a sample of 480 participants followed-up at the 6-month endpoint. Using data from other studies of substance using adolescents (Coulton S et al., 2023, Deluca et al., 2020) we estimate the prepost-test correlation of the frequency of substance use to be 0.4, and incorporating this into the sample size calculation reduces the number followed-up to 364, 182 in each group. Assuming a loss to follow-up at the endpoint of 10%, similar to other studies in adolescent substance use populations (Coulton et al., 2024) inflates the number needed to randomise to 400. Assuming 80% of those eligible will be willing to consent an indication of acceptability of the study to participants and a lower figure than other studies in similar populations (Coulton et al., 2024) would mean we would need to approach 480 across both sites. Recruitment will be continuous between September 2025 and January 2027, 28 per month will need to be approached in total across both sites per month with the expectation that 24 will consent to participate in the trial across both sites. We anticipate. Based on relative population size that 40% of referrals will come from Newport and 60% from Bristol.

Table 2: Recruitment/ retention table

	Q1	Q2	Q3	Q4	Q5	Q6	Q7	Q8	Q9	Q10	Q11
Months (e.g. Oct-Dec 23):	May-Jul 25	Aug-Oct 25	Nov 25 - Jan 26	Feb - Apr 26	May-Jul 26	Aug-Oct 26	Nov 26 - Jan 27	Feb - Apr 27	May-Jul 27	Aug-Oct 27	Nov 27 - Jan 28
Target number of children and young people referred into the project	0	50	75	75	75	75	75	75	218	360	500
Target number of children and young people recruited to the project and evaluation	0	40	60	60	60	60	60	60	174	288	400
Target number of children and young people who withdraw/drop out	0	4	6	6	6	6	6	6	23	35	40

Table 3: Sample size calculations

		PARAMETER		
Minimum Detectable Effect Size (MDES)		0.27		

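### Siblings can be randomised to opposite arms of a family therapy, and the protocol's no-contamination statement does not cover that route

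*Protocol*

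**What the plan says.** **Allocation.** Table 1 of the protocol gives the unit of randomisation as "Individual young person". The Randomisation section states that "The allocation will involve an equal probability of receiving one of the two trial arms, MDFT or BAU", in permuted blocks stratified by site and GAIN-SS severity. Household is not a factor.

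**Eligibility.** Neither the inclusion and exclusion criteria nor their repeat in Appendix I limits enrolment to one young person per household, and no rule on siblings appears elsewhere. One of the alternative at-risk factors is "Have a sibling or parent who has been involved in serious violence or identified as facing exploitation harm". Others, such as social-worker contact or care experience, can also apply to more than one child in a family.

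**Therapy.** The Study rationale describes a parent domain aimed at parenting, and a family domain aimed at better "patterns of communication and problem-solving using multi-participant family sessions". The Intervention section gives typically 4-10 parent sessions and 4-10 "family sessions where the therapist facilitates meaningful conversations among the family members who attend".

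**Contamination.** The Risks table has a row on control families receiving help from several providers. It argues that intensive family-based work is rare in UK services for young people and ends: "We do not anticipate any contamination within the study". The Business as usual section adds that BAU comes from organisations other than Barnardo's, so MDFT therapists do not deliver it.

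**Sample size.** "A clinically important effect size for substance use frequency in adolescents is estimated as 0.27". The calculation is made "with power at 80% and alpha of 0.05 and a two-tailed test", with a pre-post correlation of 0.4. It gives 364 followed up, 182 per arm. There is no allowance for contamination, and Table 3 marks the cluster level as not applicable.

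**The concern.** MDFT is delivered partly to the household. If one sibling is allocated to MDFT and another to BAU, the second lives with parents who are being treated and may be among the relatives who attend family sessions. Under intention to treat that sibling stays in the BAU arm, so any benefit they gain narrows the difference between arms.

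Both arguments against contamination concern the BAU services: what they offer and who delivers it. Neither concerns what reaches a BAU participant at home. The Risks row speaks of families in the control group, as if each family belonged to one arm, and individual randomisation does not ensure that.

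What is at stake is a modest bias towards no effect in a trial sized with almost no spare power. Monitoring of what BAU participants receive is promised only for the pilot, so later exposure might not be recorded.

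**Working it through.** **Step 1. Is the route open?** It needs three things, and the text permits each.
- Both siblings can be eligible: no criterion excludes a second household member.
- They can be split: allocation is 1:1 by individual and ignores household.
- The treatment reaches others in the home: parent and family sessions are part of MDFT, and the Equality Impact Assessment (Appendix III, Age) itself expects benefit to family members beyond the index participant.

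**Step 2. Reproduce the planned size.** Inputs from Sample size calculations: effect 0.27, two-sided alpha 0.05, power 80%, correlation 0.4.

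n per arm = 2 × (1.960 + 0.842)² × (1 − 0.4²) / 0.27² = 2 × 7.849 × 0.84 / 0.0729 = 180.9, so 181 per arm and 362 in total. The t-based version gives 363.7, so the stated 364 reproduces.

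Power at 182 per arm: 0.27 × √(182/2) / √0.84 = 2.810, and Φ(2.810 − 1.960) = 80.2%.

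**Step 3. Dilution.** Let s be the share of participants in sibling pairs. The documents do not give it, so 4%, 10% and 20% are assumed. With separate 1:1 allocation about half the pairs split, so the exposed share of the BAU arm is c = s/2. Let k be the fraction of the MDFT effect that an exposed sibling gains. Then

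observed effect = 0.27 × (1 − k × c), and power = Φ(effect × √(182/2) / √0.84 − 1.960).

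| s | Pairs among 400 | Exposed BAU participants of 200 | Full carry-over (k = 1): effect, power | Half carry-over (k = 0.5): effect, power |
|---|---|---|---|---|
| 4% | 8 | 4 (2%) | 0.265, 78.6% | 0.267, 79.5% |
| 10% | 20 | 10 (5%) | 0.257, 76.1% | 0.263, 78.2% |
| 20% | 40 | 20 (10%) | 0.243, 71.5% | 0.257, 76.1% |

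Worked line for s = 10%, k = 1: 0.27 × 0.95 = 0.2565; 0.2565 × 9.539 / 0.9165 = 2.670; Φ(0.710) = 76.1%.

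**Step 4. Numbers to restore 80% power.** With full carry-over, the normal formula that gave 362 gives 378, 402 and 448 followed up for s = 4%, 10% and 20%. With one participant per household, c from this route is zero and the planned 364 stands.

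**The case against.** **Likelihood.** A reader might infer from the sibling item in the eligibility list that siblings will often enter together. The documents do not support that. The item is one of eleven alternative risk factors, it covers a sibling or a parent, and it qualifies the young person referred, not the sibling. A sibling must separately be 13-17, live in Bristol or Newport, meet an offending or risk criterion, have used on at least four occasions in 28 days, be referred and consent. Nor is referral only through family-facing services: the Participants section and Appendix I also name Youth Justice Teams as a main route, and the Participants section adds violence reduction and exploitation arrangements. Joint entry is possible, not shown to be likely.

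**Contradiction.** A reader might say the design contradicts the Risks table. No other statement denies that sentence. It closes an argument about BAU providers and is worded more widely than the argument allows, so for the family route it is unsupported.

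**Size of exposure.** Full carry-over is an upper bound. Under Compliance, adolescent-only sessions make up 55% of the total, and a BAU sibling gets none of them. The Risks table says early work identifies which relatives take part, and a trusted adult may stand in for a parent, so a sibling's attendance is not automatic. This stands, and is why half carry-over is shown.

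**Independence.** A reader might add that siblings break the independence assumed in the analysis. They do, but the harm is not quantified. Under separate 1:1 allocation, positive correlation within a pair lowers the variance of the arm difference when the pair is split and raises it when the pair is together, so the two largely offset. The case rests on dilution alone.

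**Cost of the rule.** The Diversity, equity and inclusion section aims to keep eligibility criteria few, and a household rule works against that. This is a real though small cost.

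None of these points closes the route.

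**Conclusion.** The point holds as a cheap improvement. As written, the plan can place siblings in opposite arms of a therapy that treats their shared household, and the no-contamination statement does not address this. Any resulting bias is towards no difference.

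Its size depends on two quantities the documents do not give: how many participants are in sibling pairs, and how much of the effect carries over. Over the assumed range of 4% to 20% in pairs, power is 78.6% to 71.5% with full carry-over and 79.5% to 76.1% with half, against 80.2% planned. With few sibling pairs and partial carry-over the loss is a point or two at most, so the expected loss is probably small. The case for acting is that the remedy is simple and a split pair cannot be repaired after randomisation.

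**What to change.** - **Eligibility.** Add to the inclusion criteria, and to their repeat in Appendix I, that only one young person per household may be randomised, namely the first to complete baseline.
- **Screening.** Have Barnardo's ask at screening whether another member of the household is already in the trial. Log later siblings as screened but not randomised. A direct question is safer than matching on family name, which can miss siblings; the protocol does not say that Barnardo's holds data suited to matching.
- **Risks table.** Limit the no-contamination sentence to contamination through BAU providers, and cite the household rule for the family route.

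The cost is one eligibility line and one screening question. A few sibling referrals are lost, and one criterion is added against the stated aim of keeping exclusions to a minimum. The planned 364 followed up and 400 randomised need no change on this account.
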